9.2.4. Ankylosing Spondylitis Disease Activity Score (ASDAS_{CRP})

The ASDAS_{CRP} endpoint is derived from several patient reported outcomes and hsCRP (mg/L) which will be calculated by the sponsor. Following is the formula used for calculating the ASDAS_{CRP} (Sieper et al., 2009; Lukas et al., 2009).^{12,15}

$$ASDAS_{CRP} = 0.121 \times \text{Back Pain} + 0.058 \times \text{Duration of Morning Stiffness} + 0.110 \times \text{Patient Global} + 0.073 \times \text{Peripheral Pain/Swelling} + 0.579 \times \text{Ln}(\text{hsCRP}+1).$$

Question 2 of the BASDAI provides the data for Back Pain, Question 6 of the BASDAI provides the data for Duration of Morning Stiffness, the score from the Patient Global Assessment of Disease (PGA) is utilized for the Patient Global and Question 3 of the BASDAI contributes the data for Peripheral Pain/Swelling. If any one of the five components is missing, ASDAS_{CRP} is considered missing. The range of the ASDAS_{CRP} is ≥ 0 , with higher scores indicating greater disease activity.

hsCRP will be set to 0.199 mg/L in the formula above and in all efficacy and safety analyses, where 0.2 mg/L is the lower limit of quantification (LLOQ) of the assay.

The ASDAS_{CRP} clinically important improvement, major improvement and inactive disease will be calculated from the ASDAS_{CRP} data (van de Heijde et al. 2016).⁹

- ASDAS_{CRP} clinically important improvement is defined as a response if improvement (decrease) from Baseline in ASDAS_{CRP} ≥ 1.1 units.
- ASDAS_{CRP} major improvement is defined as a response if improvement (decrease) from Baseline in ASDAS_{CRP} ≥ 2.0 units.
- ASDAS_{CRP} inactive disease is defined as a response if actual ASDAS_{CRP} < 1.3 units.

9.2.5. Swollen Joint Count (44)

Swollen joints are recorded in the CRF page of joint swelling. This page is to be completed if answer to the question, “Does this subject exhibit any joint swelling in the physical exam?” is “Yes.” For each of the 44 joints, swelling can be recorded as “Present”, “Absent”, “Not Done”, “Not Applicable” or this joint assessment is simply missing. Before calculating the swollen joint count, the following pre-processing steps for each joint should be performed:

- If a joint receives an intra-articular injection (either at Baseline or post-baseline visits), set the joint status to “Present” on or after the date of injection regardless of the assessment of the joint recorded on the CRF page.
- If there is no associated injection record available, a joint recorded as “Not Done” is set to missing.
- A joint recorded as “Not Applicable” means that measurement cannot be made and this joint is set to missing.

After this pre-processing, a joint assessment that is set to missing is to be imputed by the average of the non-missing values of the other joints, with the restriction that the number of missing joint assessments cannot exceed 50% of the expected total number of joints evaluated for the swollen joint count (ie, 22, 50% of 44). In that case, the swollen joint count is set to missing.

Explicitly after pre-processing, let:

- N_1 =number of joints recorded as “Present”;
- N_2 =number of joints recorded as “Absent”;
- N_3 =number of joints with missing values.

The total number of joints assessed is $N_1 + N_2 + N_3$ (ie, 44). The imputed swollen joint count is therefore $N_1 + N_3 \times (N_1 / (N_1 + N_2))$ if $N_1 + N_2 > 22$; otherwise the swollen joint count is set to missing. It can be noted that the swollen joint count may not be a whole number. Note that if there is no missing joint assessment, the swollen joint count will be the number of joints recorded as “Present” (ie, N_1).

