5.8.4. Prohibited Medications

Prohibited drugs and dietary supplements not otherwise specified herein or in [Appendix 4](#) must be discontinued at least 30 days or 5 half-lives (whichever is longer) before the first dose of investigational product. A list of prohibited drugs with specific discontinuation recommendations can be found in [Appendix 4](#).

- Any DMARDs (synthetic or biologic) except for methotrexate or sulfasalazine. Subjects receiving any other investigational or marketed treatment for AS, arthritis or back pain other than permitted in [Appendix 4](#). Subjects receiving any other investigational drug during the study.
- Injected (intravenous, intramuscular, intraarticular or epidural) corticosteroids are not allowed during the blinded portion of the study either as a stable concomitant medication or as rescue medication.
- Herbals with pharmaceutical properties are allowed only if there is acceptable evidence of no CYP3A inhibition or induction and must be reported as a concomitant medication. Otherwise, herbals with pharmaceutical properties must be discontinued for at least 4 weeks prior to first dose of study drug, unless there is sufficient data available regarding the duration of an herbal medication’s pharmacokinetic and pharmacodynamic effects to allow a shorter washout to be specified (eg, 5 half-lives).
- Vaccinations with live components are prohibited during the study and for 6 weeks after last dose of investigational product.
- Currently receiving or previously used thalidomide.

- Acetaminophen/paracetamol is not permitted as a part of combination products such as over-the-counter “cold remedies” or in combination with opioids if the acetaminophen/paracetamol dose will exceed 2.6 gm/day.

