5. GENERAL METHODOLOGY AND CONVENTIONS

There will be a total of 2 planned analyses conducted when all applicable subjects have completed their Week 16 and Week 48 (including follow-up) visits, respectively. The investigators, subjects and sponsor study team will remain blinded to the first 16 weeks of treatment assignment through the entire duration of the trial until database release at Week 48. The Week 16 analysis will include all efficacy data through Week 16 and the safety data through the data cutoff date (for those subjects who have passed the Week 16 visit). As the primary endpoint (ASAS20), the key secondary endpoint (ASAS40) and the other Type I error controlled secondary endpoints are at Week 16, there will be no additional adjustment made for Type I error rate at the final analysis at Week 48. The efficacy analysis results through Week 16 obtained from the Week 16 analysis will be considered final and definitive. CCI

The Week 48 analysis will be conducted when all the applicable subjects have completed their Week 48 (including follow-up) visit and the database is released. All the Week 48 analysis results will be secondary in nature. The Week 48 analysis will contain results for earlier visits prior to or at Week 16 including those for the primary endpoint and the key secondary endpoint; however, they will serve as a sensitivity analysis only to ensure there are

no major changes to the definitive results for the primary endpoint and the key secondary endpoint obtained at the Week 16 analysis.

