9.2.6. Maastricht Ankylosing Spondylitis Enthesitis Score (MASES)

Thirteen sites are assessed for tenderness on the MASES CRF page. For each site, tenderness can be recorded as “Present”, “Absent”, “Not Done”, or this site assessment is simply missing. Before calculating MASES, the following pre-processing step for each site will be performed:

- If a site is recorded as “Not Done”, set the site to missing.

After this pre-processing, a site assessment that is set to missing is to be imputed by the average of the non-missing values of the other sites, with the restriction that the number of missing site assessments cannot exceed 50% of the expected total number of sites evaluated for the MASES (ie, 6.5, 50% of 13). In that case, the MASES is set to missing.

Explicitly after pre-processing, let:

- N_1 =number of sites recorded as “Present”;
- N_2 =number of sites recorded as “Absent”;
- N_3 =number of sites with missing values.

The total number of sites assessed is $N_1 + N_2 + N_3$ (ie, 13). The imputed MASES is therefore $N_1 + N_3 \times (N_1 / (N_1 + N_2))$ if $N_1 + N_2 > 6.5$; otherwise the MASES is set to missing. It can be noted that the MASES may not be a whole number. Note that if there is no missing site assessment, the MASES will be the number of sites recorded as “Present” (ie, N_1).

9.2.7. 36-Item Short Form Survey Version 2 (SF-36v2) Acute

The SF-36 v.2 (Acute) is a 36-item generic health status measure. It measures 8 general health domains: physical functioning, role limitation due to physical health, bodily pain, general health perceptions, vitality, social functioning, role limitations due to emotional problems and mental health. These domains can also be summarized as physical and mental component summary scores (Ware Jr et al., 2007).¹⁶

For each of the 8 domains, the raw score is first transformed into a score within the range of 0-100. This score will then be standardized into a Z-score using the domain’s mean and standard deviation based on the 1998 general U.S. population (ie, norm). This Z-score is finally re-scaled to a scale score (or norm-based score) with mean of 50 and standard deviation of 10. The scale scores (ie, norm-based scores) of the 8 domains are used for analyses. These 8 domains are as follows:

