9.2.9. Functional Assessment of Chronic Illness Therapy – Fatigue (FACIT-F)

FACIT-F is a 13-item questionnaire (each item score ranges from 0 to 4). There will be 3 endpoints derived: FACIT-F total score, FACIT-F experience domain score and FACIT-F impact domain score (Cella et al., 2002; Cella, Lai, and Stone, 2011).^{19,20} FACIT-F total score (range 0-52) is calculated by summing the 13 items. FACIT-F experience domain score (range 0-20) is calculated by summing 5 items of Q1 I feel fatigued, Q2 I feel weak all over, Q3 I feel listless (“washed out”), Q4 I feel tired and Q7 I have energy, while FACIT-F impact domain score (range 0-32) is calculated by summing the remaining 8 items. Note that all the scores except for Q7 & Q8 should be reversed (ie, 0 →4, 1→3, 3→1, 4→0) prior to

summing for both the total score and the domain scores such that higher scores represent better functioning (ie- less fatigue).

All responses are added with equal weight to obtain the total score. In cases where some answers are missing, a total score is prorated from the score of the answered items, so long as more than 50% of the items (ie, at least 7 of 13 for FACIT-F total score, at least 3 of 5 for FACIT-F experience domain score, and at least 5 of 8 for FACIT-F impact domain score) are answered.

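### Does SAP 9.2.5 leave the swollen joint count undefined after a joint injection, or when exactly 22 joints are missing?

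*SAP*

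**What the plan says.** SAP 9.2.5 starts from the joint swelling CRF page. It says "This page is to be completed if answer to the question" on any joint swelling is Yes. No count is written down for a No.

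Pre-processing of each joint comes next, ahead of the count. A joint given an intra-articular injection becomes Present "on or after the date of injection regardless of the assessment of the joint recorded on the CRF page". Joints recorded as Not Done (with no injection record) or Not Applicable become missing.

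Missing joints are then imputed from the others. The prose condition is that "the number of missing joint assessments cannot exceed 50% of the expected total number of joints evaluated for the swollen joint count", with the limit given as 22. The formula that follows uses N1 (Present), N2 (Absent) and N3 (missing). It gives a count if N1 + N2 > 22; "otherwise the swollen joint count is set to missing".

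The neighbouring enthesitis score (SAP 9.2.6) follows the same pattern: "Thirteen sites are assessed for tenderness on the MASES CRF page". It has no Yes/No entry question, and its limit is 6.5.

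**The concern.** A derivation section should let two programmers reach the same number from the same record, and here there are two places where they might not.

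- **A No after an injection.** The joint page is not completed, yet the injection rule says one joint is Present. Depending on what No is taken to mean for the other 43 joints, and when, the count could be 0, 1 or missing. A plain 0 would score an injected joint as resolved, which the injection rule is there to prevent.
- **Exactly 22 joints missing.** Read literally, the prose imputes and the formula does not. The joint list in Protocol 7.2.8 has 22 joints per side, so a page with one side unrecorded would land on this value. The visit would then be either used in an MMRM without imputation or lost from it.

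At stake are individual values of the change from baseline in the swollen joint count, and its summaries.

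**Working it through.** **The plan's own figure.** Protocol 7.2.8 lists, per side: sternoclavicular 1, acromioclavicular 1, shoulder 1, elbow 1, wrist 1, MCP 5, thumb IP 1, PIP 4, knee 1, ankle 1, MTP 5. The sum is 22, so both sides give 44, and 50% of 44 is 22, as SAP 9.2.5 states.

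**Exactly 22 missing.** The formula is count = N1 + N3 × N1/(N1 + N2).

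1. Prose: impute if N3 ≤ 22.
2. Formula: impute if 44 − N3 > 22, that is, N3 ≤ 21.
3. Over N3 = 0 to 44 (45 values) the two differ only at N3 = 22.

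With N1 = 4:

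| N3 | N2 | Prose | Formula |
|---|---|---|---|
| 21 | 19 | 4 + 21 × 4/23 = 7.65 | 7.65 |
| 22 | 18 | 4 + 22 × 4/22 = 8 | missing |
| 23 | 17 | missing | missing |

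For the enthesitis score both rules reduce to N3 ≤ 6, because 6.5 cannot be reached with whole sites. The same pattern is consistent there and produces a tie only when the total is even.

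**A No after one injected joint.** There are three candidate readings:

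| Reading of No | (N1, N2, N3) | Count |
|---|---|---|
| Count is 0, whatever the joint records say | not used | 0 |
| All 44 Absent, then the injection rule | (1, 43, 0) | 1 |
| Page blank, then the injection rule | (1, 0, 43) | missing, since 1 is not > 22 |

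1. The first reading is excluded. SAP 9.2.5 puts the injection rule among the joint-level steps done before the count, and that rule overrides a recorded finding of no swelling. A 0 applied at the end would undo it.
2. The third reading is excluded by what No means without an injection. If a blank page meant missing joints, a subject whose swelling had fully resolved would have no count at exactly that visit. That does not fit SAP 9.5 (range 0 to 44), SAP 6.5.1 (swollen joints present at baseline means a count above 0, otherwise No), SAP 4.4.1 (only a subset is expected to have swollen joints), or Protocol 7.2.8 (all 44 joints are assessed). Injecting one joint gives no reason to turn the other 43 from not swollen into not assessed.
3. The second reading remains, and the count is 1.

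**Reach.** Had a programmer used 0 instead of 1, the change from a baseline count of 2 would be −2 instead of −1, a difference of one joint per visit. Protocol 4.1 requires injected corticosteroids to stop 4 weeks before the first dose, and Protocol 5.8.4 says that injected "corticosteroids are not allowed during the blinded portion of the study". The case therefore belongs mainly to Weeks 24, 32, 40 and 48, at most 4 visits per subject, when both groups take open-label tofacitinib. Of the analysis that covers those visits, SAP 5 says "All the Week 48 analysis results will be secondary in nature". The Week 16 efficacy results are already final by then.

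**The case for a change.** The strongest case for acting is that the SAP is the document meant to remove such doubts. SAP version 4 was issued partly to settle derivation details of this kind, such as handling of hsCRP at the quantification limit and the treatment switch date. Two or three sentences would do it, with no new data. The formula is also presented as following from the prose, and at 22 missing joints it does not.

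Part of this stands. The conflict at 22 is real, and the step from No to all joints Absent is not written down. Placing pre-processing before the count does not by itself state the status of the other 43 joints; that has to be taken from other sections.

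Three things weaken the case for a change:

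- For the 22-joint tie, aligning the prose with the formula changes no value under the rule that would be programmed. The SAP's other conventions do not favour one direction. FACIT-F is prorated "so long as more than 50% of the items" are answered, but several SF-36 scales accept exactly half (Physical Functioning 5 of 10, Role-Physical 2 of 4, Vitality 2 of 4).
- A page with one side unrecorded is conjecture. The CRF layout and the joint figure are not in the documents, and nothing says such pages occur.
- For the injection case, the sentence one would add states the only reading the documents already allow.

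**Conclusion.** No change to the plan follows. The 22-joint conflict is a clerical slip at one boundary value, with an explicit formula that gives a single answer. The No-after-injection case is missing detail that an analyst would fill in the one way consistent with the rest of the plan.

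The size is bounded by where the count is used. It enters one secondary endpoint, change in the swollen joint count, restricted to subjects with a baseline count above 0 and absent from all the Type I error families in SAP 5.1. ASAS20, ASAS40 and the sample size are untouched. Per visit, the injection case is worth one joint for each injected joint if misread as 0. The boundary case is worth one visit kept or lost; at Baseline it would decide whether the subject enters the endpoint at all.

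This rests on two assumptions: that the explicit formula is what gets programmed, and that a No on the CRF records an examination in which no joint was swollen. The CRF itself cannot be checked here. The frequency of injections and of half-recorded pages is not given, so no effect on a treatment difference can be calculated. Before Week 16 the injection case would need a protocol deviation or an injection other than a corticosteroid.

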7.2.8. Swollen Joint Count (44)

The qualified blinded assessor will also assess joints for swelling using the following scale: Present/Absent/Not Done/Not Applicable (to be used for artificial or missing joints) for

determination of the total number of swollen joints. It is recommended that the same qualified personnel be used for each visit. Forty-four (44) joints will be assessed for swelling as noted in Figure 2¹¹ below and will include the following: sternoclaviculars, acromioclaviculars, shoulders, elbows, wrists, metacarpophalangeals (MCP I, II, III, IV, V), thumb interphalangeal (IP), proximal interphalangeals (PIP II, III, IV, V), knees, ankles, and metatarsophalangeals (MTP I, II, III, IV, V). Artificial joints will not be assessed.

Figure 2. 44 Swollen Joint Count Mannequin

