- Δ in extra-articular involvement (Specific Medical History and peripheral articular involvement [as assessed by Swollen Joint Count (44) (Δ SJC[44])]) at all time points (Weeks 2, 4, 8, 12, 16, 24, 32, 40, and 48) (see [Section 9.2.5](#));
- Δ in Spinal Mobility: Chest Expansion at all time points (Weeks 2, 4, 8, 12, 16, 24, 32, 40, and 48);

The chest expansion (cm) is measured as the difference between maximal inspiration and expiration. Two attempts will be performed and the better (ie, larger) of the two attempts will be utilized for data analysis.

- Δ in EuroQol-5D Health State Profile – 3 Level Version (Δ EQ-5D-3L) (5 Dimensions: Mobility, Self-Care, Usual Activities, Pain/Discomfort and Anxiety/Depression, “Your own health state today” [Δ EQ-VAS], and EQ-5D-3L Utility score based on United Kingdom (UK) weights) at Weeks 16 & 48 (see [Section 9.2.8](#));
- Δ in Work Productivity & Activity Impairment (Δ WPAI) Questionnaire: Spondyloarthritis (4 subscale scores in range of 0-100%) at Weeks 16 & 48 (see [Section 9.2.10](#)).

The 4 subscales are (1) percent work time missed due to health problem, (2) percent impairment while working due to health problem, (3) percent overall work impairment due to health problem, and (4) percent activity impairment due to health problem.

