4.4. Other Analysis Sets

4.4.1. Endpoint Specific Analysis Sets

Subjects will be excluded from the FAS for analyzing a specific endpoint if the criterion for inclusion is not met for the endpoint.

Table 2. Endpoint Specific Analysis Sets

Endpoint	Inclusion	Rationale
ASDAS _{CRP} Clinically Important Improvement (improvement [decrease] from Baseline in ASDAS _{CRP} ≥ 1.1 units)	Include subjects with Baseline ASDAS _{CRP} ≥ 1.1 units in FAS	Restrict Baseline ASDAS _{CRP} ≥ 1.1 units to allow room for response
ASDAS _{CRP} Major Improvement (improvement [decrease] from Baseline in ASDAS _{CRP} ≥ 2.0 units)	Include subjects with Baseline ASDAS _{CRP} ≥ 2.0 units in FAS	Restrict Baseline ASDAS _{CRP} ≥ 2.0 units to allow room for response
ASDAS _{CRP} Inactive Disease (ie, ASDAS _{CRP} < 1.3 units)	Include subjects with Baseline ASDAS _{CRP} ≥ 1.3 units in FAS	Restrict Baseline ASDAS _{CRP} ≥ 1.3 units to allow room for response
Δ in Swollen Joint Count (44)	Include subjects with Baseline swollen joint count (44) > 0 in FAS	Having swollen joints is not an enrollment criterion, it is expected only a subset of subjects will have swollen joints at Baseline.
Δ MASES	Include subjects with Baseline MASES > 0 in FAS	Enthesitis is not an enrollment criterion, it is expected only a subset of subjects will have enthesitis at Baseline.
Abbreviations: Δ = change from Baseline, ASDAS _{CRP} = Ankylosing Spondylitis Disease Activity Score - C-Reactive Protein, FAS = Full Analysis Set, MASES = Maastricht Ankylosing Spondylitis Enthesitis Score.		

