5.2.2. Analyses for Continuous (Repeated) Data

Repeated measures data for continuous or order-categorical (analyzed as continuous) endpoints will be analyzed as change from baseline as appropriate with a mixed model for repeated measures (MMRM) that includes fixed effects of treatment group, visit, treatment-group by visit interaction, stratification factor (ie, prior treatment history: "bDMARD-naïve" vs "TNFi-IR or bDMARD Use [Non-IR]") at randomization, stratification-factor by visit interaction, baseline value, and baseline-value by visit interaction. A common unstructured variance-covariance matrix will be used, provided the model converges, otherwise an alternative covariance structure, eg, heterogeneous compound symmetry (CSH), will be attempted. The Kenward-Roger degrees of freedom approximation will be used. This model is referred to as MMRM. Comparison of tofacitinib 5 mg BID to placebo (providing least squares means [LSM] of the treatments, LSM of the treatment difference, 2-sided p-value and 95% CI) at each time point during the first 16 weeks will be generated using this MMRM. Comparisons of tofacitinib 5 mg BID and placebo → tofacitinib 5 mg BID for visits after Week 16 through Week 48 are also reported from the same model. For each endpoint, the number of subjects by treatment group in the FAS, the number of subjects by treatment group included in the MMRM and the number of subjects by treatment group evaluable at each of the visits are also to be reported. If the Baseline is missing or if there are no post-baseline measurements, the subject will be excluded from this analysis (see [Section 4.1](#)).

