6.5. Baseline and Other Summaries and Analyses

6.5.1. Baseline Summaries

Baseline characteristics will include but may not be limited to the ones listed below and will be summarized descriptively. For continuous variables, the summary will include N (which is the number of subjects evaluable for the baseline characteristics), mean, median, SD and range (ie, minimum and maximum); for binary and categorical variables, the summary will include frequencies and percentages. A missing category will be included for those subjects with missing value. In addition to displays by treatment groups, the summaries will also be provided for all the treatment groups combined.

Demographic characteristics:

- Baseline age (2 categorizations: <18, ≥18 to ≤44, ≥45 to ≤64, ≥65 years; <18, ≥18 to ≤44, ≥45 to ≤64, ≥65 to ≤74, ≥75 to ≤84, ≥85 years; and continuous in years);
- Gender (Female, Male);
- Race (White, Black, Asian, Other);
- Geographic region (see [Section 6.4.1](#) for definition);
- Ethnicity (Hispanic/Latino, non-Hispanic/Latino);
- Baseline body weight (<60, ≥60 to ≤100, >100 kg; and continuous in kg);
- Baseline height (continuous in cm);
- Baseline waist circumference (continuous in cm);

- Baseline BMI (<18.5, ≥18.5 to <25, ≥25 to <30, ≥30 to <40, and ≥40 kg/m²; and continuous kg/m²);
- Baseline smoking status (Never Smoked, Former Smoker, Current Smoker);
- Duration of smoking started (continuous in years) for subjects who are Current Smokers or Former Smokers;
- Duration of smoking stopped (continuous in years) for subjects who are Former Smokers only;
- Baseline pack-year (continuous in pack-year) for subjects who are Current Smokers or Former Smokers;
- Baseline Alcohol use (Yes, No; continuous in units/week for subjects who have Current Alcohol use at Baseline); Yes is defined for subjects who have Current Alcohol use at Baseline, else No.

Baseline disease characteristics:

- Prior treatment history at randomization ("bDMARD-naïve", "TNFi-IR or bDMARD Use [Non-IR]") where prior treatment history is derived from the clinical database (see [Section 9.11](#)). Under the "TNFi-IR or bDMARD Use (Non-IR)" category, two subcategories: "TNFi-IR" and "bDMARD Use (Non-IR)" will be summarized. Subjects under "bDMARD Use (Non-IR)" are not TNFi-IR and have prior bDMARD Use without IR (see [Section 9.11](#));
- AS disease symptom duration (<5, ≥5 years; and continuous in years);
- AS disease duration since diagnosis (<5, ≥5 years; continuous in years);

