- Family history of Spondyloarthritis (Yes, No);
- History of Uveitis (Yes, No);
- Current symptom of Uveitis (Yes, No) for subjects with history of uveitis;
- History of Psoriasis (Yes, No);
- Current symptom of Psoriasis (Yes, No) for subjects with history of psoriasis;
- History of Inflammatory Bowel Disease (IBD) (Yes, No);
- Current symptom of IBD (Yes, No) for subjects with history of IBD;
- HLA-B27 (Positive, Negative);
- Baseline hsCRP (≤2.87, >2.87 mg/L [ie, Elevated hsCRP]; and continuous in mg/L);

- Baseline metabolic syndrome (Yes, No) (see [Section 9.7.1](#) for definition);
- Baseline diabetes mellitus (Yes, No) (see [Section 9.7.2](#) for definition);
- Baseline PGA (continuous);
- Baseline Patient Assessment of Pain – Total Back Pain (continuous);
- Baseline Patient Assessment of Pain – Nocturnal Spinal Pain (continuous);
- Baseline BASFI (continuous);
- Baseline BASDAI Total score (continuous);
- Baseline Inflammation (Average of questions 5 and 6 of BASDAI) (continuous);
- Baseline BASMI and its 5 components (continuous);
- Baseline Spinal Mobility – Chest Expansion (continuous in cm)
- Baseline AS disease activity (ASDASCRP <1.3 [inactive disease], ≥1.3 to <2.1 [low disease activity], ≥2.1 to ≤3.5 [high disease activity], >3.5 [very high disease activity] units, and continuous) (van der Heijde et al. 2016; Machodo et al., 2018);^{9,10}
- Baseline presence of enthesitis based on MASES (Yes, No). Yes is defined for those subjects with Baseline MASES >0;
- Baseline MASES (continuous) for those subjects with Baseline MASES >0;
- Baseline presence of swollen joints (Yes, No). Yes is defined for those subjects with Baseline SJC(44) >0;
- Baseline SJC(44) (continuous) for those subject with Baseline SJC(44) >0;
- Baseline SF-36v2 – 8 domain scale (ie, norm-based), PCS, MCS scores (continuous);
- Baseline EQ-5D-3L – 5 dimension scores (continuous), EQ-VAS (Your own health state today) (continuous in mm) and EQ-5D-3L Utility score (UK) (continuous);
- Baseline FACIT-F – Total score, Impact domain and Experience domain scores (continuous);
- Baseline WPAI – 4 subscores (continuous in %);
- Baseline ASQoL Total score (continuous).

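### Read literally, SAP 9.2.5 scores a visit with no joint swelling as a missing SJC(44) instead of 0 (minor)

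*SAP*

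**What the plan says.** SAP 9.2.5 puts a gate in front of the joint assessments: "This page is to be completed if answer to the question" on any swelling at the physical exam is Yes. A joint can be present, absent, not done, not applicable, or have no entry, in which case it is missing. The pre-processing steps deal with injected joints, not done and not applicable. With N1 present, N2 absent and N3 missing joints, the count is N1 + N3 × N1/(N1 + N2) if N1 + N2 > 22; "otherwise the swollen joint count is set to missing". Nothing is said about a No answer. SAP 5.3 refers the reader to 9.2.5 for missing joints and adds no further rule.

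The surrounding text treats 0 as an ordinary value:

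- SAP Table 6 gives the range as 0-44.
- SAP Table 2 defines the analysis set for change in SJC(44): "Include subjects with Baseline swollen joint count (44) > 0 in FAS".
- SAP 6.5.1 splits subjects by presence of swollen joints at baseline, where Yes means a count above 0. It also states: "A missing category will be included for those subjects with missing value".
- Protocol 7.2.8 mentions no gate: "Forty-four (44) joints will be assessed for swelling".

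Change in SJC(44) is analysed by MMRM without imputation (SAP 6.3, Table 8). SAP 5.2.2 adds: "If the Baseline is missing or if there are no post-baseline measurements, the subject will be excluded from this analysis". SAP 5.3 rests the validity of that model on MCAR or MAR data.

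**The concern.** A No answer is the record of the best possible outcome on this scale. If it leads to a skipped page, and a skipped page leads to a missing count, the derivation deletes complete resolution from the data. The subjects analysed all had swelling at baseline, so they are the ones in whom resolution would be seen.

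A value missing because it is 0 is missing because of the outcome itself. Neither the baseline covariate nor the earlier visits in the MMRM makes that MAR. The descriptive tables would not reveal the loss, because SAP 5.2 bases them on available data. At baseline, subjects without swelling would move from the No row of the 6.5.1 table to the missing row.

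MASES (SAP 9.2.6) uses the same proration formula but describes no gate question, so the gap is specific to the joint count.

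**Working it through.** **1. The plan's threshold.** 50% × 44 = 22, as stated in SAP 9.2.5. The formula needs N1 + N2 > 22, so at least 23 joints must be recorded as present or absent.

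**2. The rule applied literally.**

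| Visit | N1 | N2 | N3 | N1 + N2 | SJC(44) |
|---|---|---|---|---|---|
| Answer No, page blank | 0 | 0 | 44 | 0 | missing |
| Answer No, page blank, one joint set to present by the injection rule | 1 | 0 | 43 | 1 | missing |
| Page complete, three swollen | 3 | 41 | 0 | 44 | 3 |
| Page complete, none swollen | 0 | 44 | 0 | 44 | 0 |
| 40 absent, 4 missing, none swollen | 0 | 40 | 4 | 40 | 0 + 4 × 0/40 = 0 |

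The first row is the problem. Mapping No to 44 absent joints turns it into the fourth row, and the same formula then returns 0.

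**3. Effect on the model.** A subject with baseline count above 0 who answers No at a visit contributes nothing at that visit. The subject still contributes at any visit with a count, and leaves the model only if no post-baseline visit has one.

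**4. Illustration on assumed counts.** The documents give none. Take baseline 4 for everyone.

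*Case A: the arms differ only in the share resolved, 60% on tofacitinib and 40% on placebo; unresolved subjects have 3 joints in both arms (change -1).*

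- All values kept: tofacitinib 0.6 × (-4) + 0.4 × (-1) = -2.8; placebo 0.4 × (-4) + 0.6 × (-1) = -2.2; difference -0.6.
- Resolved visits missing: -1.0 and -1.0; difference 0.

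*Case B: same true means, but 40% resolved in both arms.* The change x in unresolved tofacitinib subjects must satisfy 0.4 × (-4) + 0.6x = -2.8, so x = -2.

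- All values kept: -2.8 and -2.2; difference -0.6.
- Resolved visits missing: -2.0 and -1.0; difference -1.0.

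The same true difference is erased in A and overstated in B. In both cases the mean improvement within each arm is understated.

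**5. Baseline adjustment does not help.** A single-visit ANCOVA was run on simulated data of the case A type: baseline 1 + Poisson(3); in unresolved subjects each joint persists with probability 0.7, with a minimum of one; treatment acts only through resolution. Resolution of 30% v 10%, 40% v 20%, 50% v 25% and 60% v 30% gave differences of -0.57, -0.57, -0.70 and -0.86 joints with zeros kept, and about 0.00 in each case with zeros missing. With 40% v 40% both were 0. The near-zero result is built into the assumed mechanism, so this shows only that conditioning on baseline does not recover the loss.

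**The case against.** The strongest reply is that this is an omitted line whose meaning is clear. A No answer is a recorded finding of no swelling, and the 50% rule, which fills a missing joint from the others, reads as written for a partly completed page. If No meant missing, the Table 2 restriction to baseline counts above 0 would do almost nothing, because SAP 5.2.2 already excludes subjects with no baseline value. A programmer would probably code 0. The CRF is also not in the documents: the system may write absent for all 44 joints on a No answer, and then the rule works.

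This establishes the intent, and it keeps the point minor. It does not supply the rule. SAP 9.2.5 counts joints recorded as present or absent and closes with an explicit default to missing. A programmer who codes 0 is departing from the written derivation, and two programmers could differ.

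A reader might also infer several stronger things that the documents do not support:

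- *That every subject whose swelling resolves is dropped.* The loss is by visit; a subject goes only if no post-baseline count exists.
- *That the rule can never produce 0.* Any page with N1 = 0 and N2 of at least 23 gives 0.
- *That the bias runs against tofacitinib, or for it.* Cases A and B go opposite ways, on assumed inputs.
- *That the sponsor chose to discard zeros.* Tables 2 and 6 and Section 6.5.1 point the other way.

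**Conclusion.** The point holds as a minor defect in the written derivation. Followed literally, SAP 9.2.5 returns a missing SJC(44) for a visit answered No with a blank page, contrary to the evident intent of the rest of the SAP. The consequence would be outcome-dependent missingness in the MMRM among subjects with swelling at baseline.

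This rests on one inference: that a No answer leaves the 44 rows blank, as the SAP's description of the page implies. The size and direction of bias in the treatment difference cannot be determined from the documents, and the figures above are illustrations only. Change in SJC(44) is a secondary endpoint outside all the Type I error families in SAP 5.1, so no primary or key secondary conclusion changes.

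**What to change.** Add to SAP 9.2.5, for Baseline and all post-baseline visits:

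> If the joint swelling question is answered No, all 44 joints are set to Absent and SJC(44) = 0, except joints set to Present by the injection rule. If the question is unanswered, SJC(44) is missing.

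The cost is two sentences of SAP text before the Week 16 unblinding, with no new data, visits, tables or tests. One side effect is that the corrected counts will contain many zeros, so the normal model fits less well; the percentage of subjects with a count of 0 by arm could be shown beside the MMRM result.
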